6.4 Criteria for premature discontinuation of trial product

The patient may be prematurely discontinued from trial product at the discretion of the investigator due to a safety concern.

The patient must be prematurely discontinued from trial product if the following applies:

1. Included in the trial in violation of the inclusion and/or exclusion criteria
2. Simultaneous participation in another clinical trial of an approved or non-approved investigational medicinal product.
3. Incapacity or unwillingness to follow the trial procedures
4. Anaphylactic reaction
5. Thromboembolic event
6. Event of disseminated intravascular coagulation (DIC)
7. Development of inhibitors to Factor VIII (≥ 0.6 BU)
8. Lack of efficacy due to neutralising antibodies towards concizumab
9. Lack of efficacy defined as ≥ 3 treated sBEs within the previous 12 weeks in patients being treated with the highest dose level (0.25 mg/kg) of concizumab.

See Section [8.1.4](#) for procedures to be performed for patients discontinuing trial product prematurely.

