Table 8–2 Definitions of bleeding episodes (cause of bleed)

Category	Definition
Spontaneous	Not linked to a specific, known action or event
Traumatic	Caused by a specific, known action or event (e.g. injury or exercise)
Post-surgical	Bleeding episodes after surgery from the surgical wound. Bleeding episodes during surgery does not fall under this category

Table 8–3 Definition of bleeding episode severity and treatment recommendation

Category	Definition	Treatment recommendation
Mild/Moderate	
Examples: uncomplicated musculoskeletal bleeding episodes (joint, muscular bleeds without compartment syndrome), mucosal- or subcutaneous bleeding episodes
 
Mild/moderate bleeding episodes may occur in other anatomical locations
	Mild/moderate bleeding episodes can be treated at home before contact to the investigator

Protocol
 Trial ID:NN7415-4255
 UTN:U1111-1179-3872
 EudraCT no.:2016-000614-29

~~CONFIDENTIAL~~

Date: 28 August 2018
 Version: 5.0
 Status: Final
 Page: 58 of 127

Novo Nordisk

Severe	
Examples: intracranial, retroperitoneal, iliopsoas and internal neck bleeding episodes; muscle bleeding episodes with compartment syndrome; bleeding episodes associated with a significant decrease in the haemoglobin level (>3g/dl)
 
Severe bleeding episodes may occur in other anatomical locations
 
Bleeding episodes that require hospitalisation
 
All life-threatening bleeding episodes
	Severe bleeding episodes must be treated immediately
Instruction for patients	The patient must be instructed to contact the investigator immediately if in doubt regarding treatment of a bleeding episode and to discuss what other actions may need to be taken	

Information about bleeding episodes prior to visit 2 will be recorded in eCRF.

The trial site should be informed of the details of all bleeding episodes, including those that are treated outside of the trial site. After visit 2 bleeding episodes must be recorded either in the eDiary (if treated at home) or in the eCRF (if treated at the trial site), see section [12.3](#).

Severity of bleeding episodes must be evaluated by the investigator according to [Table 8-3](#) and reported in the eDiary database.

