12.1 Definitions

12.1.1 Adverse event

An adverse event (AE) is any untoward medical occurrence in a patient administered a medicinal product, and which does not necessarily have a causal relationship with this treatment.

An AE can therefore be any unfavourable and unintended sign (including an abnormal laboratory finding), symptom or disease temporally associated with the use of a product, whether or not considered related to the product.

An AE includes:

- A clinically significant worsening of a concomitant illness.
- A clinical laboratory adverse event (CLAE): a clinical laboratory abnormality which is clinically significant, i.e. an abnormality that suggests a disease and/or organ toxicity and is of a severity that requires active management. Active management includes active treatment or further investigations, for example change of medicine dose or more frequent follow-up due to the abnormality.

The following should **not** be reported as AEs:

- Pre-existing conditions, including those found as a result of screening or other trial procedures performed before exposure to trial product (pre-existing conditions should be reported as medical history or concomitant illness).
- Pre-planned procedures unless the condition for which the procedure was planned has worsened from the first trial related activity after the patient has signed the informed consent.
- Bleeding episodes and other symptoms (e.g. pain, swelling, synovitis, arthralgia) in connection with bleeding episodes should not be reported as AEs/SAEs unless the event is fatal, life-threatening or evaluated by the investigator as related to trial product or trial procedure. All bleeding episodes and other findings related to underlying disease will be captured in the eCRF/eDiary

The following three definitions are used when assessing an AE:

- **Severity**
 - **Mild** – no or transient symptoms, no interference with the patient’s daily activities.
 - **Moderate** – marked symptoms, moderate interference with the patient’s daily activities.
 - **Severe** – considerable interference with the patient’s daily activities; unacceptable.
- **Causality**
 Relationship between an AE and the relevant trial product(s):
 - **Probable** - Good reason and sufficient documentation to assume a causal relationship.

Protocol
 Trial ID:NN7415-4255
 UTN:U1111-1179-3872
 EudraCT no.:2016-000614-29

~~CONFIDENTIAL~~

Date: 28 August 2018
 Version: 5.0
 Status: Final
 Page: 81 of 127

Novo Nordisk

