12.1.6 Adverse event of special interest

An adverse event of special interest (AESI) is an event, which in the evaluation of safety, has a special focus. In this trial, the following AEs fulfil the AESI criteria:

- Thromboembolic events including but not limited to,
 - disseminated intravascular coagulation (DIC) (A),
 - clinical signs or laboratory indications of arterial and venous thrombosis including myocardial infarction (B),
 - pulmonary embolism (C),
 - stroke (D),
 - deep vein thrombosis (E),
 - other clinically significant thromboembolic events (F) and peripheral artery occlusion (see below G), see definitions below.

The AESIs must be reported on an AE form and a safety information form.

Protocol
 Trial ID:NN7415-4255
 UTN:U1111-1179-3872
 EudraCT no.:2016-000614-29

~~CONFIDENTIAL~~

Date: 28 August 2018
 Version: 5.0
 Status: Final
 Page: 85 of 127

Novo Nordisk

A) Definition of disseminated intravascular coagulation (DIC), as defined below:

The definition of DIC in this trial should be made according to the International Society on Thrombosis and Haemostasis (ISTH) criteria. Thus, a DIC diagnosis may be based on clinical signs and symptoms of a bleeding tendency or thrombotic tendency, organ dysfunction and the laboratory parameters criteria as listed below:

- Platelet count ($>100 \times 10^9/L = 0$, $<100 \times 10^9/L = 1$, $<50 \times 10^9/L = 2$)
- Elevated D-dimer (no increase = 0, moderate increase = 2, strong increase = 3)
- Prolonged PT ($<3 \text{ s} = 0$, $>3 \text{ but } <6 \text{ s} = 1$, $>6 \text{ s} = 2$)
- Fibrinogen level ($>1 \text{ g/L} = 0$, $<1 \text{ g/L} = 1$)
- Calculate score: ≥ 5 compatible with overt DIC

(B) Myocardial infarction is defined according to the “Third Universal Definition of Myocardial Infarction”²⁴

Criteria for acute myocardial infarction - The term acute myocardial infarction (MI) should be used when there is evidence of myocardial necrosis in a clinical setting consistent with acute myocardial ischemia. Under these conditions any one of the following criteria meets the diagnosis for MI:

- Detection of a rise and/or fall of cardiac biomarker values [preferably cardiac troponin (cTn)] with at least one value above the 99th percentile upper reference limit (URL) and with at least one of the following:
 - Symptoms of ischemia.
 - New or presumed new significant ST-segment–T wave (ST–T) changes or new left bundle branch block (LBBB).
 - Development of pathological Q waves in the ECG.

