 - Imaging evidence of new loss of viable myocardium or new regional wall motion abnormality.
 - Identification of an intracoronary thrombus by angiography or autopsy.

Criteria for prior myocardial infarction- Any one of the following criteria meets the diagnosis for prior MI:

- Pathological Q waves with or without symptoms in the absence of non-ischemic causes. Imaging evidence of a region of loss of viable myocardium that is thinned and fails to contract, in the absence of a non-ischemic cause.
- Pathological findings of a prior MI.

Recurrent myocardial infarction - Incident MI' is defined as the individual's first MI. When features of MI occur in the first 28 days after an incident event, this is not counted as a new event for epidemiological purposes. If characteristics of MI occur after 28 days following an incident MI, it is considered to be a recurrent MI.

C) Definition of pulmonary embolism:

Protocol
 Trial ID:NN7415-4255
 UTN:U1111-1179-3872
 EudraCT no.:2016-000614-29

~~CONFIDENTIAL~~

Date: 28 August 2018
 Version: 5.0
 Status: Final
 Page: 86 of 127

Novo Nordisk

The “Clinical Practice Guideline from the American Academy of Family Physicians and the American College of Physicians” on diagnosis of venous thromboembolism recommends diagnostic imaging studies for patients with intermediate or high pre-test probability of pulmonary embolism²⁵.

Accordingly, the definition of pulmonary embolism is the following: obstruction of a pulmonary artery or one of its branches, most frequently by detached fragments of thrombus from a leg or pelvic vein, diagnosed by at least one of the following:

- Positive findings in ventilation/perfusion scan
- Positive findings in a spiral (helical) computerised tomography (CT) or angiography
- Positive findings in a magnetic resonance imaging (MRI)
- Positive findings in a pulmonary angiography

D) Definition of stroke:

The definition of central nervous infarction is according to the American Heart Association/American Stroke Association Expert Consensus Document: “An Updated Definition of Stroke for the 21st Century”²⁶.

Accordingly, the term “stroke” should be broadly used to include all of the following:

Definition of central nervous system (CNS) infarction: CNS infarction is brain, spinal cord, or retinal cell death attributable to ischemia, based on:

- 1. pathological, imaging, or other objective evidence of cerebral, spinal cord, or retinal focal ischemic injury in a defined vascular distribution; or

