- 2. clinical evidence of cerebral, spinal cord, or retinal focal ischemic injury based on symptoms persisting 24 hours or until death, and other etiologies excluded.

Note: CNS infarction includes haemorrhagic infarctions, types I and II; see “Haemorrhagic Infarction”.

Definition of ischemic stroke: An episode of neurological dysfunction caused by focal cerebral, spinal, or retinal infarction. Note: Evidence of CNS infarction is defined above.

Definition of silent CNS infarction: Imaging or neuropathological evidence of CNS infarction, without a history of acute neurological dysfunction attributable to the lesion.

Definition of intracerebral haemorrhage: A focal collection of blood within the brain parenchyma or ventricular system that is not caused by trauma. Note: Intracerebral haemorrhage includes parenchymal haemorrhages after CNS infarction, types I and II - see “Haemorrhagic Infarction”.

Definition of stroke caused by intracerebral haemorrhage: Rapidly developing clinical signs of neurological dysfunction attributable to a focal collection of blood within the brain parenchyma or ventricular system that is not caused by trauma.

Protocol
 Trial ID:NN7415-4255
 UTN:U1111-1179-3872
 EudraCT no.:2016-000614-29

~~CONFIDENTIAL~~

Date: 28 August 2018
 Version: 5.0
 Status: Final
 Page: 87 of 127

Novo Nordisk

Definition of silent cerebral haemorrhage: A focal collection of chronic blood products within the brain parenchyma, subarachnoid space, or ventricular system on neuroimaging or neuropathological examination that is not caused by trauma and without a history of acute neurological dysfunction attributable to the lesion.

Definition of subarachnoid haemorrhage: Bleeding into the subarachnoid space (the space between the arachnoid membrane and the pia mater of the brain or spinal cord).

Definition of stroke caused by subarachnoid haemorrhage: Rapidly developing signs of neurological dysfunction and/or headache because of bleeding into the subarachnoid space (the space between the arachnoid membrane and the pia mater of the brain or spinal cord), which is not caused by trauma.

Definition of stroke caused by cerebral venous thrombosis: Infarction or haemorrhage in the brain, spinal cord, or retina because of thrombosis of a cerebral venous structure. Symptoms or signs caused by reversible edema without infarction or haemorrhage do not qualify as stroke.

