12.7 Rules for putting enrolment on hold

If one of below mentioned criteria is fulfilled, enrolment of additional patients in the clinical trial program will be placed on hold. An urgent safety committee meeting will be scheduled to decide further actions. Dosing of patients on treatment may continue while further evaluation is made by the safety committee. A substantial amendment with relevant data must be submitted to the regulatory authorities to support restart of the trial.

- Significant thromboembolic event
- Event of DIC
- Anaphylactic reaction related to trial drug administration
- Death of trial patient which may be related to the trial product
- Two or more other trial product related SAEs similar in nature have been reported and/or detected by laboratory measurements
- Trends in AEs, clinical observations or laboratory parameters which raise concerns about the safety of continued treatment

Protocol
Trial ID:NN7415-4255
UTN:U1111-1179-3872
EudraCT no.:2016-000614-29

~~CONFIDENTIAL~~

Date: 28 August 2018
Version: 5.0
Status: Final
Page: 96 of 127

Novo Nordisk

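### Section 12.1.6 puts stroke in the thromboembolic AESI family but defines it to include brain haemorrhage, so a bleed that is an AE is classed as a thromboembolic event

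*Protocol*

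**What the plan says.** All references are to protocol version 5.0.

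- **12.1.6, AESI list.** There is one family, "Thromboembolic events including but not limited to" a set of lettered items. Stroke is item D. DIC is item A of the same family.
- **12.1.6, definition D.** It opens by referring to infarction, then says that the term stroke "should be broadly used to include all of the following". Among the entries are "Definition of intracerebral haemorrhage: A focal collection of blood within the brain parenchyma or ventricular system that is not caused by trauma" and "Definition of subarachnoid haemorrhage: Bleeding into the subarachnoid space". Silent cerebral haemorrhage and the strokes caused by intracerebral and by subarachnoid bleeding are also listed. No sentence restricts the AESI to ischaemic or thrombotic stroke.
- **8.3.1, Table 8-3, severe category.** "Examples: intracranial, retroperitoneal, iliopsoas and internal neck bleeding episodes". Under 17 and 17.3, all treated bleeding episodes other than re-bleeds count in the primary endpoint.
- **12.1.1.** One rule covers bleeds themselves and symptoms that go with them: "in connection with bleeding episodes should not be reported as AEs/SAEs unless the event is fatal, life-threatening or evaluated by the investigator as related". The relation meant is to the drug or to a procedure of the trial.
- **12.2.** AESIs go on the AE form and the safety information form whatever their seriousness.
- **6.4, mandatory discontinuation.** "5. Thromboembolic event", with DIC as a separate item 6.
- **12.7, enrolment hold.** "Significant thromboembolic event", with DIC as a separate bullet.

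**The concern.** A general stroke definition, which covers both infarction and haemorrhage, has been placed inside a thrombosis category in a trial of patients whose disease is bleeding. Section 18.1 discusses thrombosis at length as a potential risk of the drug, and separately names bleeding from consumption of coagulation factors as a theoretical risk. The AESI is the protocol's tool for watching the first of these. If brain bleeds enter it, a count of thromboembolic AESIs no longer shows by itself whether thrombosis occurred, and one event can be recorded both as a bleeding episode and as a thromboembolic event.

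Two practical questions follow. A site with a less severe intracranial bleed must work out whether 12.1.1 or 12.1.6 with 12.2 decides reporting. And because 6.4 and 12.7 use the word thromboembolic without defining it, a site or the safety committee may turn to 12.1.6 for its meaning.

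**Working it through.** The point rests on reading the sections against each other. The protocol gives no figure to reproduce.

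**Step 1. What definition D contains.** Leaving out transient ischaemic attack, which has its own source and paragraph, there are ten sub-definitions:

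| Type | Entities | Number |
|---|---|---|
| Ischaemic or thrombotic | CNS infarction; ischaemic stroke; silent CNS infarction; stroke from cerebral venous thrombosis | 4 |
| Headed as haemorrhage | intracerebral haemorrhage; stroke caused by it; silent cerebral haemorrhage; subarachnoid haemorrhage; stroke caused by it | 5 |
| Either | stroke, not otherwise specified | 1 |

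Four of the five haemorrhage entries exclude trauma. The plain subarachnoid entry does not. The groups also overlap at the edges: the note under intracerebral haemorrhage takes in bleeding that follows an infarct, CNS infarction includes haemorrhagic infarction, and the venous thrombosis entry includes haemorrhage caused by the thrombosis. These are bleeds with a thrombotic or ischaemic origin.

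**Step 2. Follow an event through the text.** Take a non-traumatic intracranial bleed that is treated with factor VIII and is not secondary to an infarct or thrombosis.

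- *Fatal, life-threatening or judged related.* By 12.1.1 it is an AE. By 12.1.6 D it is a stroke and so a thromboembolic AESI. By Table 8-3 and 17.3 it is also a severe bleeding episode counted in the primary endpoint. The classification as thromboembolic is unambiguous and does not fit the event.
- *None of these.* By 12.1.1 it is not reported as an AE. The description in 12.1.6 D still fits it, and 12.2 requires every AESI to be reported. The list in 12.1.6 is introduced as a list of AEs, so 12.1.1 may be meant to screen first. The text does not state that order. Silent cerebral haemorrhage, an imaging finding without a history of acute neurological dysfunction, shows the difficulty best: it is named in D, yet may meet none of the 12.1.1 conditions.

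**Step 3. The linked rules.** Neither 6.4 item 5 nor the first bullet of 12.7 cites 12.1.6 or gives its own definition. Section 12.1.6 is the only place that says what thromboembolic events comprise, which favours importing it. Against that, 6.4 and 12.7 list DIC beside the thromboembolic event, while 12.1.6 puts DIC inside the family. So the two rules do not simply adopt the 12.1.6 family. Both readings are open.

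**Step 4. An illustration of size.** Section 6.1 plans 33 patients on trial product. Exact (Clopper-Pearson) 95% intervals are:

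- 0 of 33: upper limit 1 − 0.025^(1/33) = 10.6%.
- 1 of 33 = 3.0%: lower limit 1 − 0.975^(1/33) = 0.08%; upper limit, the 0.975 quantile of Beta(2, 32), = 15.8%.

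One bleed classed as thromboembolic would move an observed proportion from 0% (0 to 10.6%) to 3.0% (0.1 to 15.8%). This is illustrative only, because the protocol names no thromboembolic incidence endpoint.

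**The case against.** The strongest reply is that the consequences are small and that broad capture is deliberate.

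- **Reporting.** AESIs are a subset of AEs, so 12.1.1 decides first and a mild, unrelated bleed never reaches the AESI list. A reader might infer that sites receive two flatly opposite instructions; the text does not go that far. What stands is that the order is left to inference, for a narrow group of events.
- **Stopping and hold rules.** A reader might infer that one brain bleed is enough to require discontinuation under 6.4 or a hold under 12.7. The documents do not support this. Neither section cites 12.1.6, both treat DIC separately from the thromboembolic event, and 12.7 adds a requirement of significance. What stands is that the term is undefined where it is used.
- **Enrolment.** Section 7 lists last patient first visit as 16 December 2017, before version 5.0 of 28 August 2018, so a hold has little left to act on in this trial. Section 12.7 does speak of the wider programme.
- **Safety summaries.** A reader might infer that the safety results cannot be interpreted. They can: 17.6.2 summarises treatment-emergent events by preferred term and lists all AEs, so a haemorrhage and an ischaemic stroke would remain distinguishable, and each AESI has a safety information form.
- **Double recording.** An event may properly be both a bleeding episode and an AE; 12.1.1 provides for it. The objection here is only to the label thromboembolic.
- **Overlap of mechanisms.** Some brain haemorrhages follow infarction or venous thrombosis, and bleeding from factor consumption is a named theoretical risk. This is a fair reason to capture brain bleeds with special reporting. It is no reason to call all of them thromboembolic.

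**Conclusion.** The classification defect holds. As written, a brain haemorrhage that qualifies as an AE is a thromboembolic AESI, although the same protocol treats an intracranial bleed as a severe bleeding episode and an efficacy outcome. Five of the ten stroke sub-definitions are headed as haemorrhage and one more may be haemorrhagic. For a bleed that is not fatal, life-threatening or related, reporting is unclear. For 6.4 and 12.7 the link is a possible reading and not an established consequence.

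The effect is on AESI classification, site reporting and the reading of the thrombosis signal. The primary analysis, the sample size and the named endpoints are untouched. The conclusion assumes that sites apply definition D as worded. The AESI form and any site guidance are not part of the document and might narrow it in practice.

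**What to change.** Amend the wording as follows.

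1. **12.1.6.** Classify and tabulate haemorrhagic stroke separately from the thromboembolic AESI, either as severe bleeding episodes only or as a separate AESI of intracranial haemorrhage if the sponsor wants special reporting. Keep in the thromboembolic family the ischaemic and thrombotic entities, including transient ischaemic attack and haemorrhage secondary to CNS infarction or to cerebral venous thrombosis. Say where stroke, not otherwise specified, belongs.
2. **12.1.1.** State which reporting rule governs intracranial bleeds, so that 12.1.1, 12.1.6 and 12.2 give one answer.
3. **Reconciliation.** The sponsor must bring 6.4, 8.3.1, 12.1.1, 12.1.6, 12.2 and 12.7 into line with that classification, and say in 6.4 and 12.7 what the term thromboembolic event covers. This point does not propose what the discontinuation or hold rule should be.

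The cost is a wording amendment and an update of the AESI form. No new data, visits or procedures are needed.

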12.1.7 Technical complaints

A technical complaint is any written, electronic, or oral communication that alleges product (medicine or device) defects. The technical complaint may be associated with an AE, but does not concern the AE itself.

Examples of technical complaints:

- The physical or chemical appearance of trial products (e.g. discoloration, particles or contamination)
- All packaging material including labelling
- Problems related to devices (e.g. to the injection mechanism, dose setting mechanism, push button or interface between pen and needle)

